## **8.2. Detecting and recording serious adverse events**

### **8.2.1. Time period for detecting and recording serious adverse events**

The time period for collecting and recording SAEs will begin at the first study visit and will end at study conclusion following last study visit for each subject. See Section [8.3](#) for instructions on reporting of SAEs.

All SAEs leading to withdrawal from the study will be collected and recorded from the time of the first study visit.

All SAEs related to the study vaccine(s) that occurred since the end of the primary study NTHi-Mcat-001 (201281) will be collected retrospectively, after informed consent is obtained.

In addition to the above-mentioned reporting requirements and in order to fulfil international reporting obligations, SAEs that are related to study participation (i.e. protocol-mandated procedures, invasive tests, a change from existing therapy) or are related to a concurrent GSK medication/vaccine will be collected and recorded from the time the subject consents to participate in the study until she/he is discharged from the study.

The time period for collecting and recording of pIMDs will begin at the first study visit and will end at study conclusion following the last study visit. See section [8.3.4](#) for instructions on reporting of pIMDs.

An overview of the protocol-required reporting periods for SAEs is given in [Table 8](#).

**CONFIDENTIAL**204913 (NTHI-MCAT-006 EXT:001)  
Protocol Amendment 1 Final**Table 8 Reporting periods for collecting safety information**

Event	Visit 1	Visit 2	Visit 3	Visit 4	Visit 5	Visit 6	Study Conclusion
	Month 20	Month 26	Month 32	Month 38	Month 44	Month 50	Month 50
SAEs							
pIMDs							
Intercurrent medical conditions*							

\* Medical conditions that, by potentially altering the immune response of a subject (except pregnancies), may lead to a subject being eliminated from analysis.

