**Blinding:**

A procedure in which one or more parties to the trial are kept unaware of the treatment assignment in order to reduce the risk of biased study outcomes. The level of blinding is maintained throughout the conduct of the trial, and only when the data are cleaned to an acceptable level of quality will appropriate personnel be unblinded or when required in case of a serious adverse event. In an open-label study, no blind is used. Both the investigator and the subject know the identity of the treatment assigned. In a single-blind study, the investigator and/or his staff are aware of the treatment assignment but the subject is not. In an observer-blind study, the subject and the site and sponsor personnel involved in the clinical evaluation of the subjects are blinded while other study personnel may be aware of the treatment assignment (see Section 5.3 for details on observer-blinded studies). In a double blind study, the subject, the investigator and sponsor staff who are involved in the treatment or clinical evaluation of the subjects and the review or analysis of data are all unaware of the treatment assignment.

Partially-blind is to be used for study designs with different blinding levels between different groups, e.g. double-blinded consistency lots which are open with respect to the control group.

**CONFIDENTIAL**204913 (NTHI-MCAT-006 EXT:001)  
Protocol Amendment 1 Final

Calendar month (Amended 28 June 2018)	A period from a specified day in one month to the day numerically corresponding to that day in the following month independently on the specific length of the month (i.e. from the 5th of February to the 5th of March)
Current smoker:	A person who is currently smoking or who has stopped smoking within the past 6 months.
Eligible:	Qualified for enrolment into the study based upon strict adherence to inclusion/exclusion criteria.
End of Study (Synonym of End of Trial):	For studies without collection of human biologicals samples or imaging data EoS is the Last Subject Last Visit (LSLV).  For studies with collection of Human Biologicals Samples or imaging data, EoS is defined as the date of the last testing/reading released of the Human Biological Samples or imaging data, related to primary and secondary endpoints. EoS must be achieved no later than 8 months after LSLV

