## 2.2. Secondary objective

- To assess the safety of the investigational NTHi-Mcat vaccine in terms of serious adverse events and potential immune-mediated diseases up to 3 years after the last planned visit (Month 14) in the NTHi-Mcat-001 study.

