6.3. Analysis of safety

6.3.1. Analysis of safety planned in the protocol

The safety analysis will be performed on the ES for safety and will include the analysis of the following categories of events:

- Serious Adverse Events (SAEs)
- pIMDs

All SAEs and pIMDs occurring at any time during the study will be recorded according to the protocol-specified reporting rules.

The verbatim reports of the symptoms will be reviewed by a physician and the signs and symptoms will be coded according to the MedDRA Dictionary for Adverse Reaction Terminology. Every verbatim term will be matched with the appropriate preferred term (PT). The number and the percentage of subjects who experienced at least one SAE with its exact 95% CI will be tabulated by group and by MedDRA PT. Same tabulation will be performed for subjects who experienced any pIMDs.

For the corresponding percentages, the denominator will be the respective numbers of exposed subjects.

SAEs or pIMDs related to the investigational vaccine administered in NTHI-Mcat-001 study, which were reported after last subject last visit of study NTHI-Mcat-001 and AFTER the subject signed the Informed Consent Form of NTHI-MCAT-006, have to be reported and included in the analyses of NTHI-MCAT-006 study.

The number of subjects who experienced any **SAE related to study participation or concurrent GSK medication/ vaccination**, from first visit up to study conclusion will be reported.

Deaths, and withdrawal due to SAE(s) reported during the entire study will be tabulated.

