8.2. Statistical considerations for interim analyses

Three interim analyses will be performed on all data obtained up to Month 20, Month 26 and Month 38, respectively. The study may be stopped if the GMC ratio (point estimate; Active [10-10-10-AS and 10-10-3-AS groups] versus PLACE2) for at least 2 out of 4 antigens is ≤ 2 , conclusion of further blood draws and early stop of the trial may be considered. Therefore, 2 GMC ratios per antigen will be calculated: 10-10-10-AS versus PLACE2, and 10-10-3-AS versus PLACE2.

- The analysis of data up to Visit 1 (Month 20) will be performed in a first step for Interim 1. This analysis will include:
 - The analysis of primary objective, as described in the section [6](#) of this document, based on the analysis of humoral immunogenicity results up to six months (Month 20) following last study visit in NTHI-Mcat-001.
 - The analysis of secondary objective, as described in the section [6](#) of this document, based on safety data collected between last visit in parent study NTHI-Mcat-001 (Month 14) and up to Visit 1 (Month 20).

This analysis will be performed on cleaned data and will be reviewed internally only. Individual listing will be provided at this stage.

If the data of the NTHI-MCAT 001 study will not be available and cleaned (freezed), an ANOVA model with only group as independent variable will be fitted instead of the planned ANCOVA model to estimate GMR between groups and placebo.

CONFIDENTIAL204913 (NTHI-MCAT-006 EXT:001)
Statistical Analysis Plan Final

- The analysis of data up to Visit 2 (Month 26) will be performed in a second step for Interim 2. This analysis will include:
 - The analysis of primary objective, as described in the section [6](#) of this document, based on the analysis of humoral immunogenicity results up to one year (Month 26) following last study visit in NTHi-Mcat-001 study.
 - The analysis of secondary objective, as described in the section [6](#) of this document, based on safety data collected between last visit in parent study NTHi-Mcat-001 (Month 14) and up to Visit 2 (Month 26).

This analysis will be performed on cleaned data and will be reviewed internally only. Individual listing will be provided at this stage.

- The analysis of data up to Visit 4 (Month 38) will be performed in a third step for Interim 3. This analysis will include:

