 - The analysis of primary objective, as described in the section [6](#) of this document, based on the analysis of humoral immunogenicity results up to one year (Month 26) following last study visit in NTHi-Mcat-001 study.
 - The analysis of secondary objective, as described in the section [6](#) of this document, based on safety data collected between last visit in parent study NTHi-Mcat-001 (Month 14) and up to Visit 4 (Month 38).

This analysis will be performed on cleaned data and will be reviewed internally only. Individual listing will be provided at this stage.

- The analysis of data up to study end will be performed in a final step for Final Analysis. This analysis will include:
 - The analysis of primary objective, as described in the section [6](#) of this document, based on immunogenicity results of each study visit.
 - The analysis of secondary objective, as described in the section [6](#) of this document, based on safety data collected between last visit in parent study NTHi-Mcat-001 (Month 14) and up to study end.

This analysis will be performed on cleaned data and be documented in a statistical report. Individual listing will be provided at this stage.

CONFIDENTIAL204913 (NTHI-MCAT-006 EXT:001)
Statistical Analysis Plan Final**9. CHANGES FROM PLANNED ANALYSES**

Not Applicable.

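### The start of safety follow-up for vaccine-related events is set by three unreconciled rules, so a related event between Month 14 and consent can be left out

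*Protocol*

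**What the plan says.** **Objective.** Protocol 2.2 and SAP 3.2 assess SAEs and pIMDs "up to 3 years after the last planned visit (Month 14) in the NTHi-Mcat-001 study".

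**SAP 8.2 (analysis window).** Every interim and the final safety analysis start at the parent-study last visit. For the final analysis the SAP says "based on safety data collected between last visit in parent study NTHi-Mcat-001 (Month 14) and up to study end". Interim 1 runs from the same start to Visit 1 (Month 20).

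**Protocol 8.2.1 (collection).** General SAE collection starts at the first visit of this study. The look-back is one sentence: "All SAEs related to the study vaccine(s) that occurred since the end of the primary study NTHi-Mcat-001 (201281) will be collected retrospectively", once consent has been given. For pIMDs, "The time period for collecting and recording of pIMDs will begin at the first study visit", and no look-back is stated.

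**SAP 6.3.1 (inclusion).** Related SAEs or pIMDs must be included if they are ones "which were reported after last subject last visit of study NTHI-Mcat-001 and AFTER the subject signed the Informed Consent Form of NTHI-MCAT-006". Both conditions concern when the event was reported.

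**Other relevant text.** SAP 11.2.1 assigns an event to the epoch by an upper limit on onset date only. Protocol 5.6.4 records conditions arising between the two studies as medical history.

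**The concern.** The objective and SAP 8.2 promise follow-up from Month 14, but the rules that decide which events are collected and included do not clearly deliver it. They differ on the start point (the subject's own visit, an undefined study end, or the parent's last subject last visit), on the date that counts (occurrence or report) and on scope (related SAEs alone, or related pIMDs as well).

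The events at risk are those judged related to an adjuvanted investigational vaccine, and Protocol 1.2.1 gives pIMD monitoring as a reason for the follow-up. A report-date rule also works in an awkward direction: the sooner a related event is notified, the likelier it is to fall before consent. Protocol 8.2.2 shows that prompt notification of related post-study SAEs is the sponsor's normal expectation in this study; if the parent protocol had a similar rule (not in these documents), such a report before consent is realistic. A table labelled as starting at Month 14 could then show too few related events.

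**Working it through.** The plan states no figure to reproduce. The check sets the rules side by side and then sizes the gap.

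| | Start | Date that counts | Related SAEs | Related non-serious pIMDs |
|---|---|---|---|---|
| Objective, SAP 8.2 | Parent last visit, Month 14 | Not specified as onset or report | Covered | Covered |
| Protocol 8.2.1 | SAEs: end of the primary study, undefined; pIMDs: Visit 1 | Occurrence | Covered from that end | No look-back |
| SAP 6.3.1 | Parent last subject last visit and this study's consent | Report | Covered if reported after both | Covered if reported after both |

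**Three cases, each with onset between the subject's Month 14 visit and consent**

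1. *Related SAE notified to the sponsor before consent.* It lies inside the SAP 8.2 window. Protocol 8.2.1 collects it if the primary study had ended for that subject. SAP 6.3.1, read literally, leaves it out because the report preceded consent. A report made before the parent's last subject last visit fails the other condition in the same way.
2. *Related SAE with onset before the parent's last subject last visit, first mentioned at Visit 1 after both SAP 6.3.1 dates.* SAP 6.3.1 includes it. Protocol 8.2.1 collects it if the end of the primary study means the subject's own last visit, but not if it means the parent's last subject last visit.
3. *Related non-serious pIMD, first mentioned at Visit 1.* The objective covers it, and SAP 6.3.1 would include it if it was reported after both dates. Protocol 8.2.1 gives no instruction to collect it, and Protocol 5.6.4 sends it to medical history. This holds under every reading of the end of the primary study.

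**Size of the window at issue**

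- Nominal gap: 20 − 14 = 6 months. Month 20 is only a label (Protocol Table 3, footnote 1), so the real gap varies by subject.
- Objective's window: 50 − 14 = 36 months. Share: 6/36 = 16.7%.
- Vaccinated subjects: up to 30 + 30 = 60. Time in the gap: at most 60 × 0.5 = 30 person-years of 60 × 3 = 180.
- Interim 1 runs from Month 14 to Visit 1, so its safety window is the gap itself. The protocol fills it only with retrospectively collected related SAEs.

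**Protocol look-back for related SAEs, by reading of its start**

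- Subject's own Month 14 visit: 0 months uncovered.
- Parent's last subject last visit: the time from the subject's own Month 14 visit to that date. It is not given; over an assumed 0 to 6 months, 0% to 16.7% of the objective's window is uncovered.

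**Effect of one omitted event (illustration, 30 per group, Clopper-Pearson as in SAP 11.1)**

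- Counted: 1/30 = 3.3%, upper 95% limit 17.2%.
- Omitted: 0/30 = 0%, upper limit 1 − 0.025^(1/30) = 11.6%.

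**The case against.** The best defence reads the documents as a coherent whole. Protocol 4.3 uses nearly the same phrase about the parent study's end in an exclusion criterion checked at entry. Protocol 5.6.4 runs medical history from parent-study completion to Visit 1, and Protocol 9.1 defines completion by the concluding visit. On that usage the phrase means the subject's own last parent visit, and the SAE look-back has no gap. Protocol 8.2.1 also requires all such related SAEs to be collected after consent, with no exception for those already notified. An event entered that way could be said to be reported after consent, and so to satisfy SAP 6.3.1. That section says which events must be included; it does not expressly exclude the rest. All analyses are descriptive, and no safety decision rule depends on these percentages.

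Much of this stands. It rules out a stronger inference that a reader might draw from the glossary, where "EoS is defined as the date of the last testing/reading released of the Human Biological Samples or imaging data", up to 8 months after last subject last visit. Applied to the parent study, that would put the look-back's start at Month 14 + 8 = Month 22 or later, after Visit 1, with all 6 months lost. Protocol 4.3 and 5.6.4 place the parent study's end before Visit 1, and a retrospective look-back from a later date would make no sense.

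The defence does not dispose of the point. It needs a favourable reading of an undefined phrase and of the word reported. It leaves SAP 6.3.1 with a report-date test that does not match the SAP 8.2 window. It does not touch the pIMD conflict.

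**Conclusion.** The inconsistency is real and should be resolved. The plan does name Month 14 as the start of safety follow-up, in the objective and in SAP 8.2. The fault is that Protocol 8.2.1 and SAP 6.3.1 do not clearly supply the events for that window. Read literally, SAP 6.3.1 can omit a related event reported before consent or before the parent's last subject last visit. Protocol 8.2.1 has no look-back for a related non-serious pIMD in a gap of nominally 6 of 36 months (16.7%).

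The loss of SAEs is conditional: some promptly notified events may be recaptured by collection after consent. A reader might also infer that such events are counted in neither study. The documents do not support that, because the parent study's safety reporting period is not in them. The change from 3.3% to 0% assumes one omitted event among 30 and predicts nothing. The conclusion concerns related events only, not the collection of unrelated events before Visit 1.

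**What to change.** **Protocol 8.2.1.** Start the related-event look-back at the subject's own Month 14 visit in NTHi-Mcat-001, and state that it covers related pIMDs, serious or not, as well as related SAEs.

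**SAP 6.3.1.** Replace the report-date test with inclusion by onset date after that visit, whenever the event was reported. Include events already notified to the sponsor as post-study events of the parent study, provided they were not already counted there. Collection and inclusion would then match the start already stated in SAP 8.2.

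**Cost.** Two wording changes and a check of the sponsor's safety database for post-study reports from the parent trial. No visits or samples are added. Event counts may become slightly less favourable.

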### **8.2.2. Post-Study serious adverse events**

A post-study SAE is defined as any event that occurs outside of the SAE reporting period defined in [Table 8](#). Investigators are not obligated to actively seek SAEs in former study participants. However, if the investigator learns of any SAE at any time after a subject has been discharged from the study, and he/she considers the event reasonably related to the vaccine(s) administered in the primary study, the investigator will promptly notify the Study Contact for Reporting SAEs.

### **8.2.3. Evaluation of serious adverse events**

#### **8.2.3.1. Active questioning to detect serious adverse events**

As a consistent method of collecting SAEs, the subject or the subject's LAR(s) should be asked a non-leading question such as:

*'Have you felt different in any way since receiving the vaccine(s) or since the previous visit?'*

When a SAE occurs, it is the responsibility of the investigator to review all documentation (e.g. hospital progress notes, laboratory and diagnostics reports) relative to the event. The investigator will then record all relevant information regarding a SAE in the eCRF. The investigator is not allowed to send photocopies of the subject's medical records to GSK Biologicals instead of appropriately completing the eCRF. However, there may be instances when copies of medical records for certain cases are requested by GSK Biologicals. In this instance, all subject identifiers will be blinded on the copies of the medical records prior to submission to GSK Biologicals.

The investigator will attempt to establish a diagnosis pertaining to the event based on signs, symptoms, and/or other clinical information. In such cases, the diagnosis should be documented as SAE and not the individual signs/symptoms.

**CONFIDENTIAL**204913 (NTHI-MCAT-006 EXT:001)  
Protocol Amendment 1 Final**8.2.3.2. Assessment of serious adverse events****8.2.3.2.1. Assessment of intensity**

The investigator will assess the maximum intensity that occurred over the duration of the event for all SAEs recorded during the study. The assessment will be based on the investigator's clinical judgement.

The intensity should be assigned to one of the following categories:

- 1 (mild) = An AE which is easily tolerated by the subject, causing minimal discomfort and not interfering with everyday activities.
- 2 (moderate) = An AE which is sufficiently discomforting to interfere with normal everyday activities.
- 3 (severe) = An AE which prevents normal, everyday activities

An event is defined as 'serious' when it meets one of the pre-defined outcomes as described in Section [8.1.2](#).

**8.2.3.2.2. Assessment of causality**

The investigator is obligated to assess the relationship between study vaccine(s) and the occurrence of each SAE using clinical judgement. In case of concomitant administration of multiple vaccines/products, if possible, the investigator should specify if the SAE could be causally related to a specific vaccine/product administered (i.e investigational, control/placebo or co-administered vaccine). When causal relationship to a specific vaccine(s)/product(s) cannot be determined the investigator should indicate the SAE to be related to all products.

Alternative plausible causes, such as natural history of the underlying diseases, concomitant therapy, other risk factors, and the temporal relationship of the event to the study vaccine(s) will be considered and investigated. The investigator will also consult the IB and/or SmPC for marketed products to determine his/her assessment.

There may be situations when a SAE has occurred and the investigator has minimal information to include in the initial report to GSK Biologicals. However, it is very important that the investigator always makes an assessment of causality for every event prior to submission of the Expedited Adverse Events Report to GSK Biologicals. The investigator may change his/her opinion of causality in light of follow-up information and update the SAE information accordingly. The causality assessment is one of the criteria used when determining regulatory reporting requirements.

If an event meets the criteria to be determined as 'serious' (see Section [8.1.2](#)), additional examinations/tests will be performed by the investigator in order to determine ALL possible contributing factors for each SAE.

**CONFIDENTIAL**204913 (NTHI-MCAT-006 EXT:001)  
Protocol Amendment 1 Final

Possible contributing factors include:

- Medical history.
- Other medication.
- Protocol required procedure.
- Other procedure not required by the protocol.
- Erroneous administration.
- Other cause (specify).

#### **8.2.3.2.3. Assessment of outcomes**

The investigator will assess the outcome of all SAEs recorded during the study as:

- Recovered/resolved.
- Recovering/resolving.
- Not recovered/not resolved.
- Recovered with sequelae/resolved with sequelae.
- Fatal (SAEs only).

### **8.3. Reporting of serious adverse events**

#### **8.3.1. Prompt reporting of serious adverse events and other events to GSK Biologicals**

SAEs that occur in the time period defined in Section 8.2 will be reported promptly to GSK within the timeframes described in [Table 9](#), once the investigator determines that the event meets the protocol definition of a SAE.

pIMDs that occur in the time period defined in Section 8.2 will be reported promptly to GSK within the timeframes described in [Table 9](#), once the investigator determines that the event meets the protocol definition of a pIMD.

